In Part 2b, each patient will be randomized to active *treatment* or placebo in each dose cohort/level in a 3:1 ratio. A dose identified from the dose-response analysis of Part 2a (based either on HBsAg decline or maximum dose evaluated and well tolerated), will be tested in different dosing regimens administered weekly (QW) or bi-weekly (Q2W). The selection of dosing regimens will be guided by the analysis of safety, PK and PD data of all previous cohorts in Part 2. A response-adaptive approach will be explored to help guide the selection of the doses to be studied based on criterion that optimizes the dose- PD response parameters (D-optimality), as well as criterion that optimizes the target dose (TD-optimality). *The total dose will not exceed 400 mg per day for Part 2c of the study.*

Part 2c is an adaptive, open-label, non-controlled, multi-arm, multi-center, study to evaluate the efficacy and safety of RO7062931 following subcutaneous administration on top of Standard of Care (SoC) therapies (a nucleoside/nucleotide analogue [NUC] with/without pegylated interferon [PEG-IFN]) in NUC-suppressed or treatment-naïve CHB patients. Both HBeAg positive and negative patients will be enrolled. Cohort 9 will enroll NUC-suppressed CHB patients and patients will receive RO7062931 on top of a NUC for up to 24 weeks. Cohort 10 will enroll NUC-suppressed CHB patients and patients will receive RO7062931 on top of a NUC plus PEG-IFN for up to 48 weeks. For Cohorts 9 and 10, RO7062931 will be administered at a dose determined from study Parts 2a and 2b. Cohorts 11 and 12 (optional cohorts) may enroll treatment-naïve immune-active CHB patients and/or different treatment combinations or treatment duration.

NUMBER OF PATIENTS

In Part 1 of the study, up to 8 cohorts of 10 HVs are planned. HVs will at each dose level be randomized to either active treatment (eight HVs per cohort) or placebo (two HVs per cohort).

For Parts 2a and 2b of the study, in CHB infected patients, a sample size of no more than 80 patients with CHB was chosen (6 patients [Part 2a] and 8 patients [Part 2b] per dose cohort).

For Part 2c, approximately 16 patients will be enrolled into the initial 2 cohorts (8 patients in each cohort). If utilized, approximately 8 patients will be enrolled to each of the Cohorts 11 and 12.

Depending on evaluation of safety, tolerability and PK data from all previous cohorts of the study, one or more additional cohorts may be studied.

TARGET POPULATION

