All doses in Part 2 will be lower than, or equal to, the doses studied and considered to be well-tolerated in Part 1. Subsequent doses and regimens for Part 2b/2c will be selected on the basis of the analysis of Part 2a data. Part 2b will be initiated once Part 2a data have been analyzed. *The* total dose will not exceed 400 mg per day.

Due to the adaptive nature of this study, the actual number of dose levels and the number of study subjects/cohorts at each dose may be modified depending on emerging data. Planned doses may be adjusted (increased, decreased, or repeated) or dosing may be discontinued. After safety and PK data review (see Section [3.1.4](#)), study subjects may be requested to return to the site for additional safety or PK assessments, upon agreement between subjects, Investigators and the Sponsor.

3.1.1.3 *Part 2c: Extended Duration of RO7062931 Therapy in CHB Infected Patients*

Part 2c is an adaptive, open-label, non-controlled, multi-arm, multi-center, study to evaluate the efficacy and safety of RO7062931 following subcutaneous administration on top of SoC therapies (a NUC with/without PEG-IFN) in NUC-suppressed or treatment-naïve CHB patients ([Figure 2](#)). Both HBeAg positive and negative patients will be enrolled.

- *Cohort 9 will enroll NUC-suppressed CHB patients. Patients will receive RO7062931 on top of a NUC for up to 24 weeks. RO7062931 will be administered at a dose determined from study Parts 2a and 2b.*
- *Cohort 10 will enroll NUC-suppressed CHB patients. Patients will receive RO7062931 on top of a NUC plus PEG-IFN for up to 48 weeks. RO7062931 will be administered at a dose determined from study Parts 2a and 2b.*
- *Cohort 11 and 12 (optional cohorts) may enroll treatment-naïve immune-active CHB patients and/or different treatment combinations or treatment duration.*

All cohorts will initially enroll approximately 8 CHB patients per cohort. Initially the enrollment will occur sequentially (Cohort 9 will be followed by Cohort 10, see Section 4.3). At the end of treatment (either 24 or 48 weeks depending on cohort), all study treatment (RO7062931 and PEG-IFN) will be discontinued and all patients will be followed up for at least 24 weeks post-treatment follow up.

Based on emerging and accumulated PK, PD, efficacy and safety data from this study or other related studies, the initial cohorts may be expanded to enroll a total of 30 CHB patients. Enrollment of the expanded cohorts may be either sequential or parallel.

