3.1.2 Dose-Review/Escalation Decisions

Dose-escalation/review meetings will be conducted by the Investigator, the Medical Monitor, and the Sponsor Clinical Team prior to each RO7062931 dose-escalation (see Section 3.1.4). The study will have an adaptive dosing design and the actual doses may be modified based on emerging safety, tolerability, PK and PD data, but with dose-escalation ratios not higher than currently projected (i.e., with more conservative escalations at higher dose levels). The decision to escalate to the next dose level, or add an additional cohort at a previously studied dose, will be made following the review of the following data from the completed cohort:

For Part 1

- All available safety information, including AEs, ECGs, vital signs, clinical laboratory test results collected up to Day 29 visit.
- All available PK data collected over ≥ 1 week post-dose to characterize the RO7062931, and if available, its metabolite(s) and predict exposure in the following cohort(s).

For Parts 2a/2b

- All available safety information, including AEs, ECGs, vital signs, clinical laboratory test results collected up to Day 57 visit (exception: Day 50 for the cohort with 4 doses given QW).
- Adequate data over the first week in Part 2a to characterize the RO7062931 PK and predict exposure in cohorts with different regimens or doses used in Part 2b.
- HBsAg levels at least by two weeks after the last dose.

For Part 2c

- *Commencement of optional cohorts, or expansion of existing cohorts, will be determined based on accumulated safety, tolerability, PK, and PD data from this study.*

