For Part 2c, the IxRS will be used to register patients to the open-label cohorts. Additionally, IxRS will be used to dispense RO7062931 and PEG-IFN for patients. The Sponsor may postpone or stop enrolment of, or only enroll certain patient subgroups, in order to evaluate pharmacodynamic parameters in different patient subgroups. The initial 8 patients of cohort 9 will be enrolled prior to the enrollment of the initial 8 patients in cohort 10. Either or both of these cohorts may be expanded up to a maximum of 30 patients in total. Assignment of patients at this expansion stage may be sequential or in parallel. Enrolment of subsequent cohorts 11 and 12 may be sequential or parallel.

The treatment allocation will be managed by the Pharmacist and will be based on the IxRS assignment.

The Principal Investigator(s) will receive a set of sealed treatment codes for Part 1. These may have the form of sealed envelopes or scratch codes. If the identity of the test medication needs to be known in order to manage the study subject's condition (in the case of a serious adverse event), the treatment code for that study subject may be broken. For Parts 2a and 2b, the Investigator(s) will be able to break the treatment code by contacting the IxRS. Treatment codes should not be broken except in emergency situations. If the Investigator wishes to know the identity of the study drug for any other reason, he or she should contact the Medical Monitor directly before the code is broken, if possible. The Investigator should document and provide an explanation for any premature unblinding (e.g., accidental unblinding, unblinding due to a serious adverse event).

Whenever disclosure of the identity of the test medication is necessary, adequate procedures will be in place to ensure integrity of the data. Any unblinding will be documented in the study report with date, reason for identifying the drug and the name(s) and role(s) in the study of the person(s) unblinded. As per health authority reporting requirements, the Sponsor will break the treatment code for all unexpected serious adverse events (see Section 5.1) that are considered by the Investigator to be related to study drug.

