6.1 DETERMINATION OF SAMPLE SIZE

In Part 1 of the study, the adaptive SAD part, the planned sample size of 8 active per cohort was chosen not only to allow adequate assessment of safety and tolerability but also to increase the precision of the estimates of mean PK and urinary parameters, [REDACTED]

Up to 80 HVs will be included in Part 1 of this study. Up to 8 cohorts of 10 HVs (8 on active and 2 on placebo per dose level) are planned but, based on the analysis of emerging PK and safety data, additional cohorts may be included or subsequent cohorts modified.

For Parts 22a and 2b of the study, the PoM in CHB infected patients, a sample size of no more than 80 patients with CHB has been chosen (6 patients [Part 2a] and 8 patients [Part 2b] per dose cohort). It is anticipated that this sample size will allow characterization of the PK/PD (viral dynamic response) relationship, as well as safety and tolerability, in patients with CHB.

For Part 2c, approximately 16 patients will be enrolled into the initial 2 cohorts (8 patients in each cohort). If utilized, approximately 8 patients will be enrolled to each of the Cohorts 11 and 12. The sample size supports the assessment of response rate of undetectable qHBsAg at Week 24 follow-up in Cohorts 10, 11, and 12.

A sample size of 8 ensures that the associated lower 90% confidence limit is above 10%, if the observed response rate is at least 38% (i.e. at least 3/8), assuming a binomial distribution. This sample size is also considered reasonable to support the safety and tolerability objectives of all cohorts, as well as to allow characterization of the qHBsAg profiles in Cohort 9. The cohorts may be expanded up to 30 subjects if warranted by emerging PD and/or safety data. A sample size of 30 ensures that the associated lower 90% confidence limit is above 20%, if the observed response rate is at least 37% (i.e. at least 11/30).

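### Is the Part 2c expansion limit of 30 patients one cap shared by Cohorts 9 and 10, so that the n = 30 precision statement in Section 6.1 cannot apply?

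*Combined protocol and SAP*

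**What the plan says.** Section 6.1, and the synopsis under Number of Patients, give the starting size: "approximately 16 patients will be enrolled into the initial 2 cohorts (8 patients in each cohort"). Section 3.1.1.3 agrees: "All cohorts will initially enroll approximately 8 CHB patients per cohort".

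Expansion is described in four places:

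- Section 3.1.1.3: "the initial cohorts may be expanded to enroll a total of 30 CHB patients".
- Section 4.3, of Cohorts 9 and 10: "Either or both of these cohorts may be expanded up to a maximum of 30 patients in total".
- Section 6.1: "The cohorts may be expanded up to 30 subjects if warranted by emerging PD and/or safety data". It continues: "A sample size of 30 ensures that the associated lower 90% confidence limit is above 20" per cent, provided at least 11 of 30 respond.
- Section 3.1.2 refers to "Commencement of optional cohorts, or expansion of existing cohorts" and gives no number.

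The synopsis gives no expansion number. On the purpose of the sample size, 6.1 states: "The sample size supports the assessment of response rate of undetectable qHBsAg at Week 24 follow-up in Cohorts 10, 11, and 12". Cohort 9 is there for its qHBsAg profiles and for safety.

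**The concern.** None of these sentences says *each* or *combined*. In 4.3 the subject can be both cohorts and the limit is qualified by *in total*, which suggests one shared allowance. Section 3.1.1.3 also speaks of *a total of 30*, although its previous paragraph writes *per cohort* for the starting size. Section 6.1 nevertheless quotes precision for n = 30.

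If the cap were shared, Cohort 10 could never reach 30. It is the only non-optional cohort for which 6.1 supports a response rate, so the n = 30 sentence would describe a size that cannot occur there. The enrolment ceiling to be set in the registration system would also differ by a factor of two.

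A second loose end concerns Cohorts 11 and 12. Sections 3.1.1.3 and 4.3 tie expansion to the initial cohorts, whereas 6.1 says only *the cohorts*, after discussing Cohorts 9 to 12.

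**Working it through.** **Inputs.** Initial size 8 in each of Cohorts 9 and 10 (3.1.1.3, 6.1); expansion number 30 (3.1.1.3, 4.3, 6.1); two-sided 90% level and targets of 10% and 20% (6.1).

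**Formula.** The exact (Clopper-Pearson) lower limit for x responders in n is the 0.05 quantile of a Beta(x, n − x + 1) distribution.

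**The plan's own figures**

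| Count | Observed rate | Lower 90% limit |
|---|---|---|
| 2/8 | 25.0% | 4.6% |
| 3/8 | 37.5% | 11.1% |
| 10/30 | 33.3% | 19.3% |
| 11/30 | 36.7% | 22.1% |

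So 3 and 11 are the smallest counts with limits above 10% and 20%, as 6.1 states. Both figures reproduce.

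**Enrolment under each reading**

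- Per cohort: Cohorts 9 and 10 reach at most 2 × 30 = 60. With Cohorts 11 and 12 at 8 each, Part 2c reaches 60 + 16 = 76.
- Shared: at most 30 for the two. After 8 + 8 = 16, 30 − 16 = 14 places remain. One cohort can reach 8 + 14 = 22, or both can reach 15. With Cohorts 11 and 12 at 8 each, Part 2c reaches 46.
- If all four cohorts could expand to 30 each, the maximum would be 120.

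**Precision under the shared reading.** The first count in each row is the smallest giving an observed rate of at least 37%, the wording in 6.1.

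| n | Smallest count at 37% or more | Lower limit | Above 20%? | Smallest count with limit above 20% |
|---|---|---|---|---|
| 15 | 6 | 19.1% | no | 7 (46.7%) |
| 16 | 6 | 17.8% | no | 7 (43.8%) |
| 17 | 7 | 21.2% | yes | 7 (41.2%) |
| 18 | 7 | 19.9% | no | 8 (44.4%) |
| 19 | 8 | 23.0% | yes | 8 (42.1%) |
| 20 | 8 | 21.7% | yes | 8 (40.0%) |
| 21 | 8 | 20.6% | yes | 8 (38.1%) |
| 22 | 9 | 23.3% | yes | 9 (40.9%) |

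Even on this reading the 37% wording holds at five of the eight sizes, including the largest. It does so because counts are whole numbers: 8/22 is 36.4%, with a limit of 19.6%, and the next count is 9.

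**Which reading fits the text**

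1. Section 4.3 opens with *either*, which applies the limit to one cohort at a time. Under a shared cap, expanding only one cohort could take it to 22 at most.
2. In 3.1.1.3 the starting size is introduced with *initially*. *A total of 30* then contrasts naturally with it: 30 counting the first 8.
3. Section 6.1 makes two parallel statements, for n = 8 and n = 30. The first is plainly per cohort, and the second follows the same form.
4. Cohort 9 receives RO7062931 with a NUC for up to 24 weeks. Cohort 10 adds PEG-IFN for up to 48 weeks. Section 6.1 does not list Cohort 9 for the response rate. A binomial statement on 30 patients pooled from both would match no stated objective.

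**The case for a change.** The best case for acting is that 4.3 governs registration and, taken alone, reads easily as a shared allowance. A ceiling of 30 against 60 is a large difference for sites and ethics committees, and adding *each* would cost almost nothing. Section 6.1 does not literally say *in one cohort* either; that is an inference from its justification.

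What stands is that the wording is not explicit and that the reach of the expansion to Cohorts 11 and 12 is unsettled. If a shared cap really was meant, the 11/30 sentence would not describe Cohort 10, and 9/22 or 7/15 would be the relevant counts.

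What does not stand is that the shared cap is the natural reading, or that a figure in 6.1 is wrong. Maximum enrolment is also open by design. Cohort sizes are approximate, Section 3.1.1.2 allows the number of subjects and cohorts to change with emerging data, and the synopsis allows additional cohorts.

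**Conclusion.** No change is needed. This is a gap in wording that a reader of 3.1.1.3, 4.3 and 6.1 together can fill: each of Cohorts 9 and 10 may grow to 30, including its first 8, for at most 60 patients. On that reading 11/30, with a lower limit of 22.1%, stands as written.

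The consequences are also limited. Section 6 makes the summaries descriptive, Section 6.11 calls the study hypothesis-generating, and 6.1 sets no test or success criterion for Part 2c. The interval will be computed on whatever number is enrolled, so the cap does not alter the analysis. Cohorts 11 and 12 are optional, and whether they may expand can be settled if they are opened.

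This rests on the per-cohort reading, which is inferred. Figure 2, the Part 2c design figure, is not visible in the text reviewed and could confirm or contradict it, and the registration-system specification is not part of the documents. Only if a shared cap was intended would the n = 30 sentence in 6.1 be out of place for Cohort 10.

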4.4 STUDY TREATMENT

4.4.1 Formulation, Packaging, and Handling

4.4.1.1 RO7062931 and Placebo

RO7062931 and placebo (IMP) to be used in the study will be provided by Roche.

[REDACTED]

[REDACTED]

[REDACTED]

4.4.1.2 Standard of Care (NUC and PEG-IFN)

As NUCs (entecavir, tenofovir alafenamide or tenofovir disoproxil fumarate) are to be used as background SoC therapies, they are classed as non-investigational medicinal product (NIMP). Please see local prescribing information for additional information.

As PEG-IFN is not licensed for use in CHB patients receiving NUC therapy, it is thus classed as an IMP.

PEG-IFN is a clear and colourless to light yellow sterile liquid provided in prefilled syringes for single use. Each prefilled syringe of 0.5 mL solution contains 180 µg peginterferon alfa-2a.

The list of excipients is as follows: sodium chloride, polysorbate 80, benzyl alcohol, sodium acetate, acetic acid, and water for injections.

The packaging and labeling of PEG-IFN will be in accordance with Roche standard and local regulations. Study drug packaging will be overseen by the Roche clinical trial supplies department and bear a label with the identification required by local law, the protocol number, drug identification and dosage. Study drug should be stored under the recommended storage conditions (2 to 8°C, protected from light). For further details, see the packaging label.

Upon arrival of investigational products at the site, site personnel should check them for damage and verify proper identity, quantity, integrity of seals and temperature conditions, and report any deviations or product complaints to the monitor upon discovery.

4.4.2 Dosage, Administration and Compliance

4.4.2.1 RO7062931 and Placebo

The qualified individual responsible for dispensing the study drug will be unblinded and will prepare the correct dose according to the randomization schedule. This individual will write the date dispensed, study subject number and initials on the study drug vial label and on the Drug Accountability Record. This individual will also record the study drug (e.g., batch number) received by each subject during the study.

SC doses will be administered at an appropriate site, for example the abdomen or upper thigh. For multiple doses, the administration site should be rotated so that the nature of any injection site reactions may be better understood (for details on dosing and dose regimen, see Section 3). All RO7062931 doses will be administered at the study clinic in

the morning by investigational staff and should be administered in the fasted state either two hours before or two hours after a morning meal. After SC administration of study drug, the Part 2 patients should remain at the site at least until the post-dose assessments are completed. The drug should be administered concomitantly with the nucleosides/nucleotides taken by the patient.

For Part 2c:

All RO7062931 administrations will be via the SC route utilizing sterile technique. RO7062931 doses will be administered SC once weekly for up to 24 weeks in Cohort 9 and for up to 48 weeks in Cohort 10. All RO7062931 doses will be administered at the study clinic in the morning by investigational staff and should be administered in the fasted state either two hours before or two hours after a morning meal.

For cohorts involving PEG-IFN, RO7062931 and PEG-IFN SC doses should be administered at different sites (e.g. left thigh and right thigh), and the administration sites should be rotated on a weekly basis between doses. This will allow to better characterize and minimize the risk of injection site reactions. For convenience, consider SC treatment administrations in the same morning as the NUC administration and PEG-IFN SC administration should be at least 1 hour after RO7062931 SC administration.

PEG-IFN administration

All PEG-IFN administrations will be administered via the SC route utilizing sterile technique. PEG-IFN at a dose of 180 µg will be administered once weekly for up to 48 weeks. PEG-IFN will be administered weekly at study clinic.

Specific guidelines for adjusting the doses of PEG-IFN for adverse event management are provided in Section 5.2.1.3. If PEG-IFN is interrupted or discontinued permanently, patients should continue treatment with RO7062931 and NUC until the end of the treatment period.

For further information on the PEG-IFN, please refer to the latest PEG-IFN Investigator Brochure.

NUC administration

NUC will be administered per local label or as per prescribing information and should be taken in the morning of RO7062931 or RO7062931 and PEG-IFN administration. NUC administration during the study, including the follow-up period, should be captured in the site documentation and eCRF. This information should include information about any missing doses during treatment and follow-up period.

For further information on the NUCs used in this study, please follow local prescribing information.

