4.7.1.1 Discontinuation from Study Drug

Study subjects must discontinue study drug if they experience any of the following:

- Pregnancy
- A serious adverse event (SAE) considered by the Investigator to be related to treatment with RO7062931.

Study subjects who discontinue study drug prematurely will be asked to return to the clinic for a study completion/early termination visit and may undergo follow-up assessments. The primary reason for premature study drug discontinuation should be documented on the appropriate eCRF.

Study subjects who discontinue study drug prematurely for safety reasons will not be replaced. Study subjects who discontinue study drug prematurely for non-safety reasons may be replaced. The Sponsor should be informed of subjects' discontinuations from the study or from the study drug.

Part 2: CHB Patients

Individual patients must discontinue RO7062931/placebo if they experience any of the following:

- Safety and tolerability issues, e.g., acute reactions, not tolerable and not manageable with symptomatic treatment.
- Grade 4 ALT (i.e., $\geq 10 \times \text{ULN}$) as defined by the Division of Acquired Immunodeficiency Syndrome (AIDS) Table for Grading the Severity of Adult and Pediatric Adverse Events ([DAIDS AE grading table](#)) confirmed within 48-72 hours (*not for Part 2c*).
- Grade 3 ALT (i.e., $> 5x$ to $< 10 \times \text{ULN}$) combined with total bilirubin $> 2 \times \text{ULN}$ (of which $> 35\%$ is direct bilirubin), or Grade 3 ALT and INR > 1.5 .
- Any other confirmed (within 48-72h) Grade 4 laboratory abnormality deemed clinically significant (based on Investigator's assessment).
- Development of liver decompensation (ascites, varices, Child-Pugh Class B or C clinical classification).
- *Grade 3 renal* adverse events defined as creatinine $\geq 50\%$ from baseline *and/or* *eGFR* $< 60 \text{ ml/min/1.73 m}^2$.
- Development of resistance in a CHB patient is suspected if the patient experiences an increase in serum HBV DNA of $> 1 \log_{10}$ (10-fold) over nadir during the treatment period, i.e., virological breakthrough.
- NUC analogue discontinuation due to safety issues or resistance development.

All prematurely discontinued patients will have assessments performed at the end of treatment with RO7062931/placebo listed in the SoAs tables. If a patient discontinues study drug between study visits, he/she should be called for an unscheduled visit to have these assessments performed.

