5.2.1.2 Alanine Transaminase (ALT) Elevations

Abrupt elevation of serum ALT above normal is known to occur spontaneously in patients with CHB during the course of disease, and/or during anti-viral therapy. Transient ALT elevations are not always harmful and may be due to:

- *The underlying disease*
- *Immune clearance of infected hepatocytes*
- *Drug-induced immune-mediated hepatitis*
- *DILI*

Isolated ALT elevations of 2-3 times the baseline value that are self-limited may reflect a desirable treatment-related immunologic response rather than drug toxicity. However, progressive increases or ALT elevations associated with increases in bilirubin without alkaline phosphatase increase should primarily be considered adverse events, i.e. potential DILI.

In the event of ALT elevation > 5x ULN, more frequent monitoring of liver tests should be performed based on medical judgment and other causes of ALT elevations should be investigated. For patients with ALT > 5 × ULN, the following management plan is recommended:

ALT elevations during treatment

- *Isolated ALT elevation with preserved hepatic function (e.g. no significant changes in bilirubin, INR/PT, albumin, and ALP):*
 - *Closely monitor liver function tests (LFTs) (i.e. ALT/AST, bilirubin, albumin, ALP and INR/PT):*
 - *ALT 5 to 10 x ULN: Repeat LFTs every week.*
 - *ALT >10 x ULN: Temporarily interrupt RO7062931 or RO7062931 and PEG-IFN treatment and repeat LFTs twice weekly until ALT level < 5 x ULN. Continue NUC treatment. Consider re-introducing RO7062931 or RO7062931 and PEG-IFN therapy following discussion with medical monitor based on subsequent laboratory results.*
- *ALT flare accompanied by declining liver synthetic and excretory functions (increased bilirubin >2 x ULN, or albumin decline >0.5 g/dL, or INR >1.5) or other signs of hepatic impairment (severe fatigue, nausea, vomiting, right upper quadrant pain):*
 - *RO7062931 or RO7062931 and PEG-IFN will be permanently discontinued, continue NUC treatment.*
 - *Closely monitor liver function tests:*
 - *ALT 5 to 10 x ULN: Repeat LFTs every week.*
 - *ALT >10 x ULN: Repeat LFTs twice weekly until ALT level < 5 x ULN.*
 - *Investigate the participant for potential etiologies of the laboratory changes.*
 - *If alternative reasons/diagnoses cannot explain the laboratory changes, a potential DILI will be considered.*

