5.2.1.3 Dose Modifications with PEG-IFN

The intention of Part 2c of the protocol is that patients remain on PEG-IFN until the completion of the allocated treatment period. However, it is possible that some patients will encounter transient or prolonged adverse effects or abnormal laboratory values at some juncture during their participation in the trial leading to potential need for adjustment of the PEG-IFN dosage.

If severe adverse reactions or laboratory abnormalities develop during PEG-IFN therapy, the dose should be modified until the adverse reactions abate. If intolerance persists after dose adjustment, PEG-IFN therapy should be discontinued.

When dose modification of PEG-IFN is required for adverse reactions (clinical and/or laboratory), an initial dose reduction to 135 mcg (adjustment to the corresponding graduation mark for the prefilled syringes) is recommended. Dose reduction to 90 mcg (adjustment to the corresponding graduation mark for the prefilled syringes) may be needed if the adverse reaction persists or recurs. Following improvement of the adverse reaction, re-escalation of the dose may be considered. [Table 1](#) provides guidelines for dose modifications and discontinuation of PEG-IFN for haematological laboratory abnormalities.

Table 1 PEG-IFN Hematological Dose Modifications Guidelines

Laboratory Values	Recommended Dose
ANC < 750 cells/mm ³	Reduce to 135 mcg
ANC < 500 cells/mm ³	Discontinue treatment until ANC values return to more than 1000 cells/mm ³ . Reinstigate at 90 mcg and monitor ANC.
Platelets < 50,000 cells/mm ³	Reduce to 90 mcg
Platelets < 25,000 cells/mm ³	Discontinue treatment

For patients who discontinue PEG-IFN early due to intolerability or if stopping criteria are met, then NUC and RO7062931 should be continued up to 48 weeks. The reasons for discontinuation of PEG-IFN and length of treatment duration will be recorded in the eCRF.

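### In PEG-IFN cohorts, the unqualified instruction in protocol 4.4.2.1 to continue RO7062931 contradicts the ALT plan in 5.2.1.2 in two situations and the liver stopping criteria in 4.7.1.1, and nothing says which governs.

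*Combined protocol and SAP*

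**What the plan says.** Four places in the current protocol body bear on what happens to RO7062931 when a patient on the combination has PEG-IFN withheld.

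- **4.4.2.1, PEG-IFN administration:** "If PEG-IFN is interrupted or discontinued permanently, patients should continue treatment with RO7062931 and NUC until the end of the treatment period". The sentence before it gives the only cross-reference: "Specific guidelines for adjusting the doses of PEG-IFN for adverse event management are provided in Section 5.2.1.3". Neither 5.2.1.2 nor 4.7.1.1 is mentioned there.
- **5.2.1.3, PEG-IFN dose modification:** "For patients who discontinue PEG-IFN early due to intolerability or if stopping criteria are met, then NUC and RO7062931 should be continued", for up to 48 weeks. The section does not define its stopping criteria, and this sentence says nothing about interruption.
- **5.2.1.2, ALT elevations:** the plan for ALT above 5 x ULN is introduced with "the following management plan is recommended". For ALT above 10 x ULN with liver function preserved: "Temporarily interrupt RO7062931 or RO7062931 and PEG-IFN treatment and repeat LFTs twice weekly". For a flare with raised bilirubin, falling albumin, raised INR or symptoms of hepatic impairment: "RO7062931 or RO7062931 and PEG-IFN will be permanently discontinued, continue NUC treatment". ALT of 5 to 10 x ULN with preserved function calls for weekly liver tests only.
- **4.7.1.1, Part 2 patients:** RO7062931 must be stopped for, among other things, ALT between 5 and 10 x ULN combined with raised bilirubin or with INR above 1.5, and for liver decompensation. The Grade 4 ALT criterion is expressly switched off for Part 2c.

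**The concern.** The trigger in 4.4.2.1 is the interruption or stopping of PEG-IFN, for whatever reason. In a PEG-IFN cohort, 5.2.1.2 itself produces that trigger when it withholds both drugs. A site that follows 5.2.1.2 and then reads 4.4.2.1 literally is told to withhold RO7062931 and to continue it in the same patient. The pointer in 4.4.2.1 does not help, because it leads to a second continuation sentence and not to the liver rules.

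Two sites could each follow a written instruction and handle the investigational drug in opposite ways during a liver event. That is a safety matter first. It also affects interpretation. Safety and tolerability are the primary objective (2.1), Part 2c has no concurrent control (3.2.3), and cohort expansion rests on accumulated data, including safety (3.1.2). In a cohort of 8, one patient handled differently is 1/8 = 12.5% of the exposure and discontinuation summary.

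**Working it through.** The plan states no figure to reproduce. The check applies each section to the same Cohort 10 patient, using only thresholds printed in the protocol. It takes the phrase in 5.2.1.2 that names RO7062931 alone or RO7062931 with PEG-IFN to mean whichever regimen the patient's cohort receives, so both drugs in Cohort 10.

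| Illustrative patient on RO7062931 + NUC + PEG-IFN | 5.2.1.2 | 4.7.1.1 | 4.4.2.1 | 5.2.1.3 |
|---|---|---|---|---|
| ALT 12 x ULN, function preserved | Interrupt both (recommended) | ALT criterion not applicable in Part 2c | Continue RO7062931 | Silent on RO7062931 during interruption |
| ALT 7 x ULN, albumin down by more than 0.5 g/dL | Stop both permanently | ALT combinations not met on these facts | Continue RO7062931 | Unclear |
| ALT 7 x ULN, INR 1.6 | Stop both permanently | RO7062931 must stop | Continue RO7062931 | Unclear |
| ALT 7 x ULN, function preserved | Monitor weekly | Not met | Not triggered | Not triggered |

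Reading across:

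1. Row 1 is a conflict between 5.2.1.2 and 4.4.2.1 only.
2. Row 2 is a conflict between the same two sections, now over a permanent stop.
3. Row 3 sets 4.4.2.1 against both 5.2.1.2 and 4.7.1.1. The 4.7.1.1 criterion acts on RO7062931 alone, so 4.4.2.1 is engaged only because 5.2.1.2 stops PEG-IFN as well.
4. Row 4 has no conflict, because PEG-IFN is not withheld.
5. In rows 2 and 3, 5.2.1.3 conflicts only if a liver event counts as intolerability or falls within its undefined stopping criteria.

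**Size.** Dosing is weekly, with the last dose at Week 48 in Cohort 10. For a permanent stop after the Week 12 dose, the readings differ by at most 48 - 12 = 36 RO7062931 doses (Weeks 13 to 48). Week 12 is an illustration. In general the maximum is 48 minus the week of the last dose given. In row 1 the difference is the number of weekly doses falling within the interruption, which the protocol does not fix.

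**The case against.** The strongest reply is that the sections can be read together. The 4.4.2.1 sentence sits under PEG-IFN administration, directly after a pointer to PEG-IFN dose adjustment, so it may be meant only for PEG-IFN withheld on its own for PEG-IFN toxicity. Section 5.2.1.2 is the specific liver rule and names RO7062931. The wording of 4.7.1.1 is mandatory, while 4.4.2.1 uses should. There are also safeguards. Isolated ALT or AST at or above 10 x ULN is reportable within 24 hours (5.1.3), re-introduction follows discussion with the medical monitor (5.2.1.2), safety concerns go to the sponsor immediately (3.1.4), and the investigator may stop RO7062931 at any time (4.7.1). All of this lowers the practical risk. It does not remove the contradiction, because no sentence limits 4.4.2.1 or ranks it below the other sections.

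Some stronger readings are tempting, but the documents do not support them:

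- A reader might infer that 5.2.1.3 contradicts 5.2.1.2 just as plainly, since it says "then NUC and RO7062931 should be continued up to 48 weeks". That sentence covers only early PEG-IFN discontinuation for intolerability or undefined criteria. It is ambiguous for liver events.
- A reader might infer that all of 5.2.1.2 is binding. The plan is introduced as a recommendation, although its permanent-stop line is worded firmly.
- A reader might infer a matching conflict for low platelets, because 4.7.1.1 also lists "Any other confirmed (within 48-72h) Grade 4 laboratory abnormality deemed clinically significant". That depends on a DAIDS platelet grade the protocol does not reproduce, and on confirmation and investigator judgement. It is not relied on here.

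**Conclusion.** The protocol is internally inconsistent on this point and should be corrected. The inconsistency is confined to cohorts receiving PEG-IFN and to two ALT situations under 5.2.1.2: above 10 x ULN with preserved function, and a flare with falling function or signs of hepatic impairment. It extends to 4.7.1.1 where one of its liver criteria is met and PEG-IFN is stopped as well.

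It can reach any affected patient among about 8 in Cohort 10 (at most 30 if expanded), plus Cohorts 11 and 12 if they are opened with PEG-IFN. The documents give no flare rate, so the number of patients affected cannot be estimated. The 36-dose figure is a ceiling for one illustrative permanent stop and should not be applied to temporary interruptions.

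The conclusion rests on reading 4.4.2.1 literally and on the cohort-regimen reading of 5.2.1.2, which is the natural one but is not stated. No view is taken on which clinical instruction is right.

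**What to change.** Reconcile the passages by amendment:

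- In 4.4.2.1 and 5.2.1.3, state which reasons for interrupting or stopping PEG-IFN the continuation sentence covers, and cross-refer to 5.2.1.2 and 4.7.1.1.
- In both places, say which section governs RO7062931 when PEG-IFN is interrupted or stopped for a liver event.
- In 5.2.1.3, define the stopping criteria or point to where they are defined.

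The choice of governing rule belongs to the sponsor's clinical team. The cost is a few sentences of protocol text, with no new assessments, patients or analyses.
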